## 2. Schedule of Activities (SOA)

Visit #	Visit 1	Visit 2	Visit 3	Visit 4	Visit 5	Visit 6	Visit 7	Visit 8	Visit 9	Visit 10	Visit 11	Visit 12
Visit Description	Pre-bronch/Screen	Baseline bronch	Randomize	Safety F/U	Safety F/U	4 week F/U	Safety F/U	8 week F/U	Safety F/U and Pre-bronch	End of study bronch	Study End	Washout End
Week (from randomization)	-4 to 0	-1	0	+1	+2	+4	+6	+8	+10	+11	+12	+16
Randomization			X									
Baseline history	X											
Physical exam	X	X	X	X	X	X	X	X	X	X	X	X
Interim history and adverse event recording		X	X	X	X	X	X	X	X	X	X	X
Blood draw (routine/safety)	X			X	X	X	X	X	X		X	X
Blood draw (biomarkers)	X		X			X		X			X	X
Blood (PK)			X@	X	X	X		X	X		X	
Pregnancy test	X		X	X	X	X	X	X	X		X	X
ECG	X		X@	X	X	X		X	X		X	X
Sputum biomarkers	X										X	
Spiro- pre and post BD			X			X					X	X
Spiro – post BD	X								X			
PROs#			X			X					X	X
Bronchoscopy		X								X		
Phone contact		X (day after)								X (day after)		
Electronic diary	X		X	X	X	X	X	X	X	X	X	X

#Patient reported outcomes to include Modified Medical Research Council questionnaire (MMRC), COPD assessment test (CAT), St George Respiratory Questionnaire (SGRQ), San Diego Shortness of Breath Questionnaire; @ pre-dose and between 1 and 2 hours post-dose

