# 4.3 Secondary Efficacy Endpoints

Blood pharmacodynamic markers of neutrophil activation and elastase activity. Change from baseline in the following outcomes at end of the treatment within patient and compared to placebo:

- 1. Plasma desmosine/isodesmosine (only change compared to placebo; withinindividual change is the primary outcome)
- 2. Plasma Aa-Val-360
- 3. Serum NE activity
- 4. Plasma proteinase 3
- 5. Plasma cathepsin B
- 6. Plasma CRP
- 7. Plasma IL-6
- 8. Plasma IL-8
- 9. Plasma IL-1b
- 10. Plasma RANTES
- 11. Plasma LTB4
- 12. Plasma MMP9
- 13. Plasma MMP12
- 14. Plasma MPO
- 15. Plasma PGP
- 16. Plasma PK/PD (LCG/DDS)

The above list was revised from the original protocol as a result of lack of data from sputum and BAL collections due to restrictions during the COVID pandemic. Data on NE may not be available on all subjects.

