# 6.2 Key Definitions

	57
Terminology	Definition
Baseline value	defined as the last non-missing value prior to first study treatment dose
End of Treatment (EOT) Visit	visit refers to the final day of study treatment administration including cases of premature discontinuation of the study treatment.
End of Treatment (EOT) Value	Last non-missing post-baseline value under study treatment.
Treatment Period	duration that a subject is under treatment in the study between the date of first study treatment intake and the date of last study treatment intake.
Study duration (in days), time to day of last visit or the day of study termination	Calculated as: Date of Safety follow-up (FU) visit (or EOT visit in case of premature discontinuation) – Date of Baseline (Day 0) + 1.
Study Completion and Withdrawal	
 
A subject will be defined as "completed the study" if subject completes the follow-up at Week 16 – either having completed, all or partially, the protocol defined visits before Week 16.
 
Termination/withdrawal at a different time point will be considered as study discontinuation/withdrawal.
 

EndPoint value	considered the value at Week 12 or EOT value (last non-missing post-baseline value under treatment)
Relative change from baseline	defined as percentage change from baseline Calculated as: [(Post-baseline value – Value at baseline)/ Value at baseline]x100%

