# 8.2 Secondary Efficacy Endpoint Analyses:

Percent change from baseline in the following outcomes at end of the treatment within patient and compared to placebo:

- 1. Plasma desmosine/isodesmosine (only relative change compared to placebo; within-individual change is the primary outcome)
- 2. Plasma Aa-Val-360
- 3. Serum NE activity
- 4. Plasma proteinase 3
- 5. Plasma cathepsin B
- 6. Plasma CRP
- 7. Plasma IL-6
- 8. Plasma IL-8
- 9. Plasma IL-1b

Plasma RANTES
 Plasma LTB4
 Plasma MMP9
 Plasma MMP12
 Plasma MPO
 Plasma PGP
 Plasma PK/PD (LCG/DDS)

The same approach, i.e., mixed modelling, will be used to analyse the change from baseline within and between treatments for the secondary outcomes using available data based on the schedule of collection and analyses. The analysis will be conducted using the SAS 'proc mixed', with the specific code given below. For each outcome, p-value<0.05 for pairwise comparisons of the least squared means between treatment groups will indicate treatment effect. This will be done for each outcome.

proc mixed data=Data; class SUBJID TRTP AVISIT SMOKING; model PCTCHG = BASE TRT|AVISIT FEV1 AGE SMOKING; ddfm=KENWARDROGER; repeated AVISIT/ subject=SUBJID type=UN; lsmeans TRTP\*AVISIT / pdiff; run;

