# 8.5.1 Presentation of Concentration Data

# 8.5.1.1 Handling of Missing Data

Plasma concentrations below the lower limit of quantification (LLOQ) of the assay are designated as NQ (not quantifiable) in the PK data and will be replaced by half value of LLOQ in listings. Values above the ULOQ will be replaced by 1.5\*ULOQ. This approach will be used for non-PK data as well.

Samples taken far outside the sampling windows and any other protocol deviation related to plasma concentration measurements will be discussed but will be excluded from summary tables. Missing values due to bad sample or unable to measure will also be excluded for that visit. Other non-missing data from the same subject will be included in the analyses.

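### SAP 4.3 and 8.2 list what appears to be alvelestat concentration as a secondary efficacy outcome, tested as percent change from a pre-dose baseline against placebo

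*SAP*

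**What the plan says.** SAP 4.3 gives the last secondary efficacy endpoint as "16. Plasma PK/PD (LCG/DDS", and SAP 8.2 repeats it, as "Plasma PK/PD (LCG/DDS", at the end of its list of 16 outcomes. LCG and DDS are not in the abbreviation list.

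SAP 8.2 sets one analysis for the whole list: "Percent change from baseline in the following outcomes at end of the treatment within patient and compared to placebo". It then gives the decision rule: "For each outcome, p-value<0.05 for pairwise comparisons of the least squared means between treatment groups will indicate treatment effect". Item 1 (desmosine) has its own qualification in both lists. Item 16 has none.

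SAP 6.2 supplies the definitions. Relative change is "defined as percentage change from baseline", with the baseline value as divisor, and baseline is "defined as the last non-missing value prior to first study treatment dose". In the protocol's Schedule of Activities, the randomisation-visit PK sample is taken "pre-dose and between 1 and 2 hours post-dose".

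SAP 6.1 sets biomarker values below the LLOQ to half the LLOQ. SAP 8.5.1.1 says of unquantifiable drug concentrations that they "will be replaced by half value of LLOQ in listings".

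Elsewhere the SAP treats drug concentration differently. Section 8.5.1.2 presents it for the alvelestat group only, and 8.3 and 8.5 relate it to responsive biomarkers by correlation. Protocol section 4 and SAP 4.4 both class the PK/PD relationship as exploratory.

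**The concern.** A drug concentration is not an efficacy outcome. No patient has study drug on board before the first dose, and a placebo patient has none at any time. A percent change from that baseline has no meaningful divisor. A comparison with placebo only asks whether patients given alvelestat have alvelestat in their plasma. Yet 8.2 would label a significant result a treatment effect, in the same list as the neutrophil elastase and inflammation markers.

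The SAP also gives PK/PD two ranks, secondary in 4.3 and exploratory in 4.4. The note under 4.3 explains the revised list by missing sputum and BAL data, which does not account for adding this item, and SAP section 10 does not declare the addition.

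**Working it through.** The documents give no figure for this item, so there is none to reproduce.

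**1. What the item is.** SAP Table 1 gives its visits as 3 to 6, 8, 9, 11 and 12. The Blood (PK) row of the Schedule of Activities has visits 3 to 6, 8, 9 and 11. The two match except for Visit 12. At visits 4, 5 and 9 the schedule has a PK draw but no biomarker draw. Protocol 9.6 and SAP 8.4 define PK sampling as measurement of alvelestat concentration. Drug concentration is therefore a strong inference, not a stated fact.

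**2. Size of the percent change.** With baseline set to half the LLOQ and an on-treatment concentration C:

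percent change = 100 × (C − 0.5 × LLOQ) / (0.5 × LLOQ)

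C = 300 nM is the level that protocol 5.5 expects to be exceeded. The LLOQ is not given and is assumed.

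| Assumed LLOQ | Half-LLOQ baseline | Percent change at 300 nM |
|---|---|---|
| 0.5 nM | 0.25 nM | +119,900% |
| 1 nM | 0.5 nM | (300 − 0.5)/0.5 = 599, so +59,900% |
| 10 nM | 5 nM | (300 − 5)/5 = 59, so +5,900% |
| 50 nM | 25 nM | +1,100% |

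The same concentration gives answers that differ about a hundredfold (119,900/1,100 = 109), depending only on the assay. A placebo patient who stays below the limit has 100 × (0.5 × LLOQ − 0.5 × LLOQ)/(0.5 × LLOQ) = 0% at every visit, with no variance.

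**3. Chance of p<0.05.** With placebo variance zero and 30 per arm, the pooled variance is s²/2, where s is the active-arm SD. The standard error is √(s²/2 × 2/30) = s/√30. Because the baseline is small against C, the t statistic is centred near √30/CV: 18.3 at CV 30%, 5.5 at CV 100% and 2.7 at CV 200%. The CV is assumed.

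Simulation used 20,000 trials, lognormal active concentrations with mean 300 nM, LLOQ 1 or 10 nM, and a two-sided pooled t-test at 0.05:

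| CV | 30 per arm | 15 per arm |
|---|---|---|
| 30% and 50% | 100% | 100% |
| 100% | 99.98% | 99.5% |
| 150% | 99.4% | about 96% |
| 200% | about 97% | about 89% |

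The choice of LLOQ hardly affects these rates, although it sets the size of the effect.

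**4. The covariate.** If every baseline is half the LLOQ, BASE is constant. A design matrix with intercept, BASE and treatment then has rank 2 for 3 columns, so BASE cannot be estimated apart from the intercept and adjusts for nothing.

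**5. Where the calculation cannot be done.** If unquantifiable values were taken as zero, the percent change would be undefined. SAP section 8 also places baseline at V1, where Table 1 shows no sample for this item. If placebo samples are not assayed, there is no comparator.

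**The case against.** The best defence is that this is a stray list entry, not an intended test. Concentrations have their own sections, shown for the active arm only. SAP 14.1 plans no mixed-model table for PK/PD, and 14.2 plans no percent-change figure for it. That may well describe the intention. It does not settle the text, because 14.1 has no table for plasma PGP either, and PGP is plainly a secondary biomarker. The secondary-endpoint listing in 14.3 names PK/PD.

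The identity of the item can also be questioned. Apart from Visit 1, its visits equal the PK and biomarker rows combined, which would suit a joint PK and PD label. That uncertainty stands. But visits 4, 5 and 9 can supply only PK, the PD markers have their own entries, and a joint quantity would need a definition that the SAP does not give.

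Four stronger readings are tempting, and the documents do not support them:

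- *The analysis divides by zero.* The half-LLOQ rule makes the divisor arbitrary, not zero. The doubt is only that 8.5.1.1 states the PK substitution for listings.
- *Significance is guaranteed.* It is near-certain under assumed CVs, by a simple t-test and not the specified mixed model.
- *The result would count towards trial success.* No rule counts significant secondary outcomes, and SAP 6.6 calls the study signal-seeking and makes no multiplicity adjustment.
- *The extra Visit 12 is part of the same fault.* Visit 12 is Week 16, and SAP section 8 limits efficacy to baseline and Weeks 4, 8 and 12. It is a separate schedule discrepancy.

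**Conclusion.** The point holds as a defect in the written plan. Read literally, SAP 4.3 and 8.2 require a test that carries no efficacy information, on a scale set by the assay limit, with a near-certain positive result if placebo samples are assayed and no possible result if they are not. The sizes rest on assumptions the documents do not fix: that item 16 is alvelestat concentration, the LLOQ, the between-patient CV, a mean of 300 nM, and placebo patients staying below the limit.

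The consequence is limited. One of 16 secondary outcomes would be mislabelled as evidence of effect, and a reader would probably recognise it as confirmation of dosing. The primary analysis and the sample size are untouched. This is a low-severity correction, worth making because the sections contradict one another.

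**What to change.** Remove the PK/PD item from the secondary efficacy lists in SAP 4.3 and 8.2, and from the secondary-endpoint listing in 14.3. Keep concentrations where they are already handled, in 8.3 to 8.5, as active-arm summaries and exposure-response analyses. This also restores the exploratory rank in protocol section 4 and SAP 4.4. Define LCG/DDS wherever the label remains.

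Separately, reconcile Visit 12 for this item in SAP Table 1 with the Blood (PK) row of the Schedule of Activities.

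The cost is a few text edits. No sampling, sample size or primary analysis changes.

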# 3.5 Inclusion-Exclusion Criteria and General Study Population

### 3.5.1 Inclusion Criteria

Participants are eligible to be included in the study only if ALL of the following criteria apply:

Type of Participant and Disease Characteristics

- 1. Capable of giving signed informed consent as described in Appendix 3, which includes compliance with the requirements and restrictions listed in the informed consent form and in this protocol
- 2. Age  $\geq$ 18 and  $\leq$ 80 years
- 3. Patients with a confirmed diagnosis of AATD: Pi\*ZZ, Pi\*SZ, Pi\*null, or another rare phenotype/genotype known to be associated with either low (serum AAT level <11 μM or <57.2 mg/dL) or functionally impaired AAT including "F" or "I" mutations.
- 4. FEV1 ≥25% predicted
- 5. Patients will be eligible if they are either a) are not currently receiving augmentation treatment and have not received augmentation in the 12 weeks prior to screening or b) have received weekly infusions of augmentation at 60 mg/kg for at least 12 weeks prior to screening and intend to continue augmentation through the study period.
- 6. Male or female sex
  - a. Male participants must agree to use a highly effective contraception as detailed in Appendix 5 during the treatment period and for at least 4 days after the last dose of study treatment and refrain from donating sperm during this period
  - b. Female participants are eligible to participate if not pregnant; not breastfeeding; and at least one of the following conditions is met:

i. Not a woman of childbearing potential as defined in Appendix 5 OR

ii. A woman of childbearing potential who agrees to follow the contraceptive guidance in Appendix 5. During the treatment phase and for at least 4 days after the last dose of study medication.

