# 6.3 Covariates and Subgroups

Prespecified covariates have been provided in the above efficacy analyses. Covariates to be included in the primary and secondary efficacy analyses on change in the biomarkers are baseline values, age and smoking history. Although we have stratified randomization by genotype, we will not include genotype as a covariate in the main analyses. Depending on available data, we may be able to compare outcomes between genotypes, but this will be exploratory in nature.

Due to the change in protocol to drop augmentation therapy from the exclusion criterion, subgroup analyses between those enrolled with and without augmentation will be performed as secondary analyses.

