# 7.3 Medical History and Concomitant Diseases

Medical history will be defined as any clinically significant past medical conditions that ended before screening. Medical history will be summarised for the SAF by treatment arm and overall with number and percentage of subjects with at least one medical history item, and number and percentage of subjects by system organ class (SOC) and preferred term (PT). The terms will be sorted by descending frequency across all subjects of SOC and then, within SOC, by descending frequency across all subjects for PT.

Relevant AATD medical history will be based on the information provided at the screening visit. The characteristics will be presented by treatment arm and overall for the SAF. The following will be tabulated:

- Genotype of AATD
- Alpha-1 level (mg/dl)
- COPD (yes/no)
- Liver Disease (yes/no)
- Cirrhosis (yes/no)
- Augmentation Therapy (yes/no)
  - Continue augmentation therapy for study duration (yes/no)
  - Asthma (yes/no)

•

- Lung cancer (yes/no)
- Bronchiectasis (yes/no)
- CV issue in last 6 months (yes/no)
- Severe/uncontrolled CHF (yes/no)
- Supplemental oxygen use (yes/no) If yes on supplemental oxygen
  - o amount prescribed (≤1 liter/min, 2 liters/min, 3 liters/min, 4 liters/min, ≥5 liters/min)
  - o duration per day (<12 hrs/day vs 12-23 hrs/day)
  - years prescribed (0-2, 3-5, 6+)
  - Screening or Historical FEV1% predicted
- AECOPD within the last year (yes/no)

lf yes,

- Number of exacerbations
- o Number of hospitalizations related to AECOPD

Medical History ongoing at start of study will be summarised separately.

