# 8.1 Primary Efficacy Endpoint Analyses:

The primary outcome is the relative change from baseline at week 12 in plasma desmosine/isodesmosine levels within treatment group. Within individual relative (percent) change from baseline in plasma desmosine/isodesmosine levels will be analyzed using Mixed Model Repeated Measures (MMRM). Relative change (percent) from baseline will be considered the response variable, with time as main independent fixed effect variable and baseline levels, augmentation, age, and smoking history (yes/no) as a fixed effect covariates, using an unstructured covariance matrix to model the within-subject errors. Available data from all time points will be included. The least squared estimates of the mean at each Week and EndPoint will be generated. [Note: Originally, it was planned to use sputum strata and FEV1 as covariates in the model. However, due to the restrictions of the pandemic, there was limited opportunity to collect the required sputum, and therefore will not be included in the analyses.] The analysis will be conducted using the SAS 'proc mixed', with the below specific code:

proc mixed data=Data; by TRTP; class SUBJID TRTP AVISIT AUGMENTATION SMOKING; model PCTCHG = BASE AVISIT AUGMENTATION AGE SMOKING; ddfm=KENWARDROGER; repeated AVISIT/ subject=SUBJID type=UN; lsmeans AVISIT / pdiff; run;

where PCTCHG is the relative (percent) change from baseline, BASE are baselines values, TRT is treatment arm, AVISIT is Weeks, AGE is age at enrollment, SMOKING is yes/no at enrollment and AUGMENTATION (yes/no) at enrollment. If imbalances are found between treatment groups in baseline characteristics deemed to be clinically important in influencing the relative change in the outcome, sensitivity analyses will be performed by including these variables as covariates in the above model. P-value<0.05 for the mean difference at Week 12 will be deemed significant. Estimate including 95% confidence interval of the least squares mean difference will also be provided.

If any issues related to convergence occur and cannot be resolved within the 'proc mixed', then alternative procedures will be considered (such as 'proc glimmix'). Other covariance structures will also be considered if convergence is an issue with unstructured covariance. Transformation of data or alternative distribution for the model will be considered should there be evidence of nonnormality of the data.

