# 8.3 Exploratory Efficacy Endpoint Analyses:

The following exploratory efficacy endpoints will be analysed using MMRM. For data that may not follow a normal distribution, we will consider either using an appropriate transformation to approximate normality or using the generalized linear model (e.g., for categorical outcomes) utilizing the generalized estimating equations or generalized linear mixed model with random intercept to address correlation of repeated measures from the same subject. Appropriate distribution based on the outcome will be chosen to fit the chosen model.

- Change from baseline in pre-and post-bronchodilator forced expiratory volume in 1 second (FEV1), forced vital capacity (FVC), FEV1/FVC (total and percent predicted), and maximal mid-expiratory flow at end of treatment. The analyses of this outcome will be dependent on the amount of spirometry data available.
- Change from baseline in St. George's Respiratory Questionnaire (SGRQ) (total and subscales), COPD Assessment Test (CAT), Modified Medical Research Council Questionnaire (MMRC), San Diego Breath Questionnaire (SOBQ) and daily symptom scores

Pearson (or Spearman rank) correlation of select biomarkers shown to be responsive to treatment with time-matched drug concentrations and PK parameters, if available, will be used to evaluate exposure-response relationship.

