# 10 Changes from Analysis Planned in the Protocol

In Version 1.3 of the protocol, augmentation therapy was removed from the list of not allowed treatment. Sample size calculation was revised but sample size remained the same. Also, stratified analyses by augmentation therapy will be performed.

Due to the risk during the COVID pandemic, spirometry as well as sputum and BAL collections were changed to optional. Consequently, all analyses using spirometry, sputum biomarkers, and BAL biomarker outcomes and data will no longer be performed in this study.

Primary analysis in the protocol is based on ANCOVA with outcome being the percent change at Week 12 from baseline. However, to minimize the effect of missing data and to maximize the information from all visits, the primary analysis is now based on fitting a mixed model using change from baseline at all available follow-up visits as outcome with the assumption of missing at random for missing data.

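### The SAP's only written-out drug-versus-placebo model (8.2) carries an undefined FEV1 covariate, disagrees with 6.3 and 8.1 on covariates, and will not run as coded

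*SAP*

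**What the plan says.** SAP 6.3 sets the covariates for both levels of analysis: "Covariates to be included in the primary and secondary efficacy analyses on change in the biomarkers are baseline values, age and smoking history". It handles augmentation through subgroup analyses.

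SAP 8.1, the primary analysis, is run separately by treatment arm. Its code reads "model PCTCHG = BASE AVISIT AUGMENTATION AGE SMOKING; ddfm=KENWARDROGER". A note there says "Originally, it was planned to use sputum strata and FEV1 as covariates in the model"; the code contains neither.

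SAP 8.2 says the secondary biomarkers, including desmosine versus placebo, follow the same mixed-model approach. Its model line is "model PCTCHG = BASE TRT|AVISIT FEV1 AGE SMOKING". The CLASS and LSMEANS statements name TRTP, not TRT. A between-group p-value below 0.05 counts as a treatment effect for each outcome, and that sentence names no visit.

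On spirometry, SAP 10 says that "all analyses using spirometry, sputum biomarkers, and BAL biomarker outcomes and data will no longer be performed in this study", while 8.3 keeps lung function as an exploratory outcome: "The analyses of this outcome will be dependent on the amount of spirometry data available". An FEV1 from entry should exist: eligibility requires "FEV1 ≥25% predicted", and 7.3 tabulates "Screening or Historical FEV1% predicted".

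**The concern.** Because 8.1 fits each arm on its own, it cannot show that a change in desmosine is due to the drug. The protocol's between-group ANCOVA (Protocol 10.3.1) was replaced as the primary analysis by SAP 10, and SAP 8.3 names a method without giving a model. The 8.2 model is therefore the only specified source of randomised evidence on desmosine, and on every other secondary biomarker.

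Three sections give it three covariate sets, and one covariate has no visit, bronchodilator status or unit. Someone must choose among them, and must also rewrite the code before it runs. If that happens with data in hand, the adjusted between-group estimate is no longer fully prespecified. If the FEV1 chosen comes from the optional study spirometry, patients without it drop out of the comparison altogether.

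**Working it through.** **Covariates side by side**

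| Term | SAP 6.3 | SAP 8.1 code | SAP 8.2 code |
|---|---|---|---|
| Baseline value | yes | yes | yes |
| Age | yes | yes | yes |
| Smoking | yes | yes | yes |
| Augmentation | subgroups only | yes | no |
| FEV1 | no | no | yes |
| Treatment | not addressed | no (run by arm) | yes |

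On augmentation, 8.1 is the section that departs from 6.3. On FEV1, it is 8.2. The variable definitions after the 8.1 code cover the other model terms but not FEV1.

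**Code, read against PROC MIXED syntax** (not executed in SAS)

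- MODEL contains TRT; CLASS and LSMEANS contain TRTP. LSMEANS therefore asks for an effect that is not in the model. If TRT is numeric, its absence from CLASS also makes it a continuous term.
- A semicolon closes MODEL before the degrees-of-freedom option, in 8.1 as well as 8.2. That option then stands alone as an invalid statement.
- For desmosine, Aa-Val-360 and NE activity there are three post-baseline visits in the efficacy window (Weeks 4, 8 and 12). Two arms by three visits give 6 means and C(6,2) = 15 printed differences. Three compare the arms at the same visit, and one of those is Week 12. The other 12 biomarkers in SAP Table 1 have only Visit 11 after baseline, so the question does not arise for them.

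**Power for desmosine, drug versus placebo**

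Inputs from SAP 3.5.3: baseline mean 0.466, SD 0.09, correlation 0.5, a 15% difference, 30 per arm, two-sided 5%. The mean, SD and correlation are stated there for the paired test and on the absolute scale, so the results approximate a percent-change analysis.

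- Difference: 0.15 × 0.466 = 0.0699.
- SD of change: 0.09 × √(2 × (1 − 0.5)) = 0.090.
- Residual SD after adjusting for baseline: 0.09 × √(1 − 0.5²) = 0.0779.
- Noncentrality: (0.0699 / SD) × √(n/2), with the noncentral t on 2n − 2 degrees of freedom (unadjusted) or 2n − 3 (baseline-adjusted).

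The plan's own figure is 82%. These inputs give a noncentrality of 3.008 and power of 84.1% unadjusted. An SD of change near 0.0925 would give 82%. The gap is small, the inputs are not stated for that test, and it is not raised as an error.

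**If patients without FEV1 are dropped.** The shares below are assumptions.

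| Missing FEV1 | n per arm | Unadjusted | Baseline-adjusted, as in 8.2 |
|---|---|---|---|
| 0% | 30 | 84.1% | 92.7% |
| 10% | 27 | 80.0% | 89.8% |
| 20% | 24 | 75.0% | 86.0% |
| 30% | 21 | 69.0% | 80.9% |
| 40% | 18 | 61.9% | 74.3% |

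**Leaving augmentation out.** If it explains an assumed 5% or 10% of the residual variance, including it at 30 per arm (2n − 4 degrees of freedom) raises power from 92.7% to 93.8% or 94.9%.

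**Chance imbalance.** Neither document stratifies randomisation by augmentation. With 60 patients, 30 per arm, and 18, 30 or 42 of them augmented (an assumed 30%, 50% or 70%), the hypergeometric probability that the arms differ by 6 or more augmented patients (6/30 = 20 points) is 15.8%, 19.6% or 15.8%.

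**The case against.** - **The code faults are typographical.** SAP 8.1 defines TRT as treatment arm, so the intent is clear, and the errors would halt the run rather than give a wrong estimate silently. This stands for the syntax. It does not settle the covariates, which are an analyst's choice.
- **The FEV1 loss is hypothetical.** An entry FEV1 should exist for nearly everyone, and no document gives a missing share. This stands: the power table is an illustration, and on the favourable reading little or nothing is lost. The plan still does not say which FEV1 it means.
- **Aligning everything to 6.3, without augmentation, would also be consistent.** True, and leaving augmentation out does not bias a randomised comparison on average. Including it is preferred because 8.1 already does so, the status is recorded, and it recovers some precision.
- **Imbalance is already covered.** SAP 8.1 adds imbalanced baseline variables as covariates in a sensitivity analysis, and SAP 6.3 and 10 plan analyses by augmentation. The 8.1 provision refers to the by-arm model, which has no treatment contrast and already contains augmentation. Extending it to 8.2 rests on the general statement that the approach is the same. Subgroup results do not adjust the overall estimate.
- **Week 12 is implied.** SAP 4.3 and 8.2 refer to end of treatment, and section 8 defines the endpoint value as Week 12 for completers. This largely stands; the missing visit is a matter of detail that one sentence closes.
- **There is time to correct it blinded.** SAP 3.6 keeps the blind until unblinding is authorised, and Protocol 10.3 requires a final SAP before database lock. That is a reason to make the correction then, not to leave it.

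**Conclusion.** The concern holds and should be fixed. Two parts rest on the text alone: 6.3, 8.1 and 8.2 give three different covariate sets, with FEV1 in 8.2 undefined and at odds with the 8.1 note and SAP 10; and the 8.2 code cannot produce the contrast it requests.

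The numerical cost is conditional. It is near zero if FEV1 is the screening or historical value. If optional study spirometry is meant, baseline-adjusted power falls from 92.7% to between 89.8% and 74.3% for an assumed 10% to 40% missing. Omitting augmentation costs about 1.1 to 2.2 points (93.8 − 92.7 and 94.9 − 92.7) under assumed explained variance, with a 16% to 20% chance of a 20-point imbalance under assumed prevalence. The main harm is the unspecified choice in the only randomised efficacy comparison.

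**What to change.** 1. State one covariate set in 6.3, 8.1 and 8.2: baseline value, augmentation, age and smoking. Delete FEV1 from 8.2.
2. Replace the 8.2 code with:
   - `class SUBJID TRTP AVISIT AUGMENTATION SMOKING;`
   - `model PCTCHG = BASE TRTP|AVISIT AUGMENTATION AGE SMOKING / ddfm=kr;`
   - `repeated AVISIT / subject=SUBJID type=un;`
   - `lsmeans TRTP*AVISIT / diff cl;`
3. In 8.1, make the degrees-of-freedom option part of MODEL, after a slash.
4. Add to 8.2: *The treatment effect is the active-minus-placebo LS mean difference at Week 12, with its 95% confidence interval and p-value; contrasts at other visits are descriptive.* The corrected code still prints all 15 differences where there are three visits, so this sentence is what fixes the test.
5. If FEV1 adjustment is still wanted, make it a sensitivity analysis using the screening or historical percent-predicted value in 7.3. Genotype, which 6.3 openly leaves out, could be another.

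The cost is SAP wording and code. Augmentation uses one degree of freedom, offset by removing FEV1, and its status is already collected at screening. The change should be made before unblinding.
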